1.2 What are the methodologies that you will employ in the study?

Study Design

A non-randomised, pre-test post-test controlled trial will be conducted to answer the research questions. The participants in the intervention group will participate in the Learning Street, while the control group receives no intervention and continues with their regular curriculum. None of the participants is subjected to an intervention as part of this study, as children in the intervention group would also have participated in the Learning Street if the present study would not have taken place. The trial is non-randomised, as the intervention group consists of all study years five who participated in the Learning Street for the first time during school year 2019-2020.

School classes in the control group will be waived from a pool of primary schools already participating in a larger study. This larger study examines the implementation process of various health-promoting initiatives at primary schools. As this study is a process evaluation, no intervention is imposed but the implementation process is followed. Schools participating in this research are free to choose if, when and how they want to implement health-promoting initiatives in their school context. Some schools participating in this research are not planning to implement any health-promoting initiatives any time soon. Therefore, these schools can serve as control schools in the present study, as they will continue with their regular curriculum for the duration of the present study. In these control schools, children from study year five and their parents will be informed about the larger study, including the measurements that will be used for the present study. Subsequently, they are asked to give their consent for their child to participate in the study. Where possible, the control schools are matched to the intervention school classes with regard to potential confounders such as school location and number of students.

Participants

Participants are students from study year five (age 8-10 years) of primary schools located in Northern Limburg, the Netherlands. Researchers and employees of Kids University for Cooking BV will inform children about the study. Information brochures are distributed and parents are asked to give permission for their children to participate in the study. Informed consent will be obtained from all parents of participating children.

Kokkerelli Learning Street

The Kokkerelli Learning Street focusses on one of the following nine products: kale, tomato, asparagus, pepper, strawberry, blue berry, mushroom, carrot, or leek. An overview of the different components of the Kokkerelli Learning Street is presented in Table 1 (1).

Table 1. Overview of the Kokkerelli Learning Street

Intervention Component	Description	Duration and Location	Materials	Delivery Channel
1. Introduction lesson	Before the introduction lesson, children are asked to fill in a questionnaire to measure their baseline taste preferences, knowledge, skills, intentions, attitude and intake regarding the Learning Street product. During the introduction lesson, children are introduced to (the taste of) the product. Children are familiarised with growing and harvesting processes, as well as with the importance of the product regarding health.	45 minutes at school	
• Preparation of the product (e.g., three types of mushrooms)• Poster of the food guide pyramid• Poster with information on unnecessary food wastage• PowerPoint presentation for assistance during the lesson• Materials to fill in the questionnaires	Delivered by the responsible teacher, with help of guidelines provided by Kids University for Cooking Foundation BV

2. Visit to the grower's farm	During the visit to the grower's farm, children are introduced to the precise planting, growing and harvesting procedures of the product. Children are allowed to enter the facilities (e.g., the greenhouse) and to closely observe and experience the farming of the product.	60 minutes at the grower's farm	No necessary material	Delivered by the farmer in cooperation with Kids University for Cooking Foundation BV
3. Cooking	Children observe and listen to the chef, while he/she explains each step that has to be taken for the preparation of the meal. Subsequently, children prepare their own portion of the meal with help of volunteers. After preparing the meal, children help to set the table and consume their self-prepared meal.	60-90 minutes at the cooking facilities of the local museum	
 • Cooking facilities such as a kitchen. • Cutting boards and knifes suitable for children. • Ingredients for the pre-chosen meals. 	Delivered by a trained chef, assisted by two volunteers
4. Evaluation lesson	Children evaluate the Learning Street together. Directly after the evaluation lesson, children are asked to answer the same questionnaire that they filled in before the introduction lesson.	45 minutes at school	Materials to fill in the questionnaires	Delivered by the responsible teacher

Schools are free to plan the different components of the Learning Street in a way that suits their schedule. However, all components should be followed within a three-week period. Usually, the introduction is planned on a separate day. The visit at the grower's farm, the food processing and the cooking take place on the same day. Lastly, the evaluation lesson is again planned on a separate day.

Measures and Data Collection Instruments

Measures in the intervention group are performed before the start of the introduction lesson (T0), directly after finishing the evaluation lesson (T1) and three months after the evaluation lesson (T2). In the control group, a similar timing of the measurements will be utilised. At baseline, participants' demographic characteristics (age in years, gender (1=male, 2=female), (parental) birth country (1=western, 2=non-western) are collected via child-reported questionnaire. At all timepoints, children are asked to answer a short questionnaire assessing their psychosocial determinants (knowledge, taste preferences, intention, skills, and attitude) related to the food product that they encountered during their participation in the Learning Street. A timeline of the Kokkerelli Learning Street and measurements can be seen below (Figure 2). In the control classes, the same questionnaires are administered following the same timeline, although children do not participate in the Learning Street.

[figure not shown]

Figure 2. Timeline of the Kokkerelli Learning Street and measurements

Psychosocial Determinants - Questionnaire

Children's knowledge will be assessed by six questions based on what they were taught during the Learning Street. Three questions are developed regarding the taste preferences (e.g., '*What do you think about the taste of the food product?*') (scale from 1='never tried' to 6='I like it very much'). Questions assessing intention concern participants' plans to consume or cook a meal containing the specific food product in the future and will be assessed on a scale from 1='I don't know' to 6='yes I will'. As the Learning Street also contains a cooking session, children are asked if they are able to cook a meal with the specific food product ('I don't know', 'no', 'a little', 'yes') to assess their skills. Questions and scales for attitude ('*How much do you think the target behaviours are clever/interesting and nice/cool/tasty?*') are used as described by Ajzen and Fishbein and as previously used in comparable research. They are formulated in a way that is simple and understandable for children (scale from 1='no, not at all' to 5='yes, totally') (8,9). The questionnaires were previously used in a pilot study on the Learning Street and appeared appropriate after small adaptations (10).

Teachers of participating school classes will be visited by Kids University for Cooking BV (intervention group) or researchers (control group) and they will receive a box with envelopes containing the three questionnaires (T0, T1, T2) for every child in their class. For each child, these questionnaires contain a unique ID number (equal for T0-T2 to allow for comparison over time) that cannot be traced back to the child. Teachers write the child's name on the envelope and at each time point, they distribute the right questionnaire to the right child. The questionnaires will be filled out in writing under supervision of the teacher, who will receive written and verbal instructions by researchers and/or employees of Kids University for Cooking regarding the questionnaire procedures. After the questionnaires are filled in, they are collected by the teacher and stored in a separate envelope in the box.

Data Processing and Statistical Analyses

After the T2 measurement, the envelopes with filled-in questionnaires are collected by Kids University for Cooking BV (intervention group) or researchers (control group). The envelopes with the ID number and name of the child, in which the blank questionnaires were stored, are not collected and will remain at the school. This means that only anonymised data will be collected, all non-anonymised data (envelopes with ID number and child's name) will remain at school. Researchers therefore only have access to the anonymised data. All anonymised data will be delivered to the principal researcher at Maastricht University.

In the data analyses, the mean scores of the answers on the questions will be used. Since single unrelated questions will be asked to test different aspects of knowledge, a score of correct answers will be used in further analyses of this determinant.

Data will quantitatively be analysed using IBM SPSS Statistics for Windows (version 25, IBM Corp, Armonk, NY, USA). Numerical variables will be presented as mean \pm standard deviation (SD), where number (%) will be used for categorical variables. A two-tailed test is considered statistically significant with p-values ≤ 0.05 . Questionnaire items for the determinants knowledge, intention, attitude, skills and taste preferences are combined into one variable per determinant for each time point. Differences in numerical baseline parameters between the control and intervention group will be tested with the independent-samples t-test or Mann-Whitney U-test where appropriate, while the Chi-square test, or Fisher's exact test, will be used for categorical variables. To investigate the in-

tervention effect on children's determinants, mean scores on the various determinants will be calculated. Then, change scores (i.e., the difference in mean score between the baseline measurement and the follow-up measurements) will be calculated. Linear mixed model analyses will be used to assess the longitudinal effect of the intervention on the various determinants assessed in the questionnaire, as this method corrects for correlation within individuals within groups, which occurs in repeated-measures research designs. Another advantage of this technique is that it naturally handles missing values, in case data are missing at random. Since measurements are repeated within participants, who are nested within classes, we use a three-level model with classes as third level, participants as second level and measurements as first level. The fixed part of the model consists of group (intervention versus control), time (time-points at which the measurements are taken) and the interaction term group*time. Baseline variables that are related to missing data and/or outcome will also be included to obtain unbiased results and/or to gain precision. As for the random part of the model, a random intercept on class level will be included next to an unstructured covariance structure for the repeated measurements. Relative effect sizes will be calculated for each determinant. These will be expressed as Cohen's d: a Cohen's d of 0.2 is interpreted as a small, 0.5 as a medium and 0.8 as a large effect size (11).

1.3 How will humans be participants in the study (either directly or indirectly, for example, through the use of their personal data)?

All children from the intervention and control classes whose parents have given their consent are asked to fill in the questionnaires. Only anonymised data will be collected and used in the present study.

1.4 Does your study re-use data that has already been gathered for another project or purpose? If so, do you have permission to re-use that data, and was there the relevant consent for this re-use in the first study? (Please explain, with reference to, for example, previous ethics committee decisions and informed consent protocols.)

In intervention classes, the data used in this study is collected as part of the Kokkerelli Learning Street. As only anonymised data will be used in the present study, the GDPR does not require the draft of a data transfer agreement or any other comparable agreement between Maastricht University and Kids University for Cooking BV.

In control classes, data is collected as part of another, larger study that will take place at the same time (further specified in an earlier section of this application). Ethical approval for this larger, ongoing study is under assessment by the Zuyderland Medical Ethics Committee. For both the intervention and control group, only data of participants whose parents/caregivers have given informed consent will be used in the present study. All anonymised data will be property of Maastricht University. The non-anonymised data (envelopes with ID number and child's name) are property of the school and will therefore remain at school after data collection to be destroyed.

1.5 What sort of people will be involved? (For example, professionals in the course of their profession, members of the general public.)

Participants will be children aged 8-10 years old (study years five) from primary schools in Limburg, the Netherlands. Parents of these children will be informed by Kids University for Cooking BV (intervention group) or researchers from Maastricht University (control group) about the study. They will receive an information brochure about the study and are asked to give written consent for their child's participation in the study.

1.6 On what grounds did you determine the number of participants needed for the study?

As one of the primary aims of the Kokkerelli Learning Street is to improve children's knowledge with regard to fruit and vegetables, it is expected that the Kokkerelli Learning Street will have positive effects on participants' knowledge. Therefore, the sample size calculation was based on the primary outcome, i.e. to detect a difference in knowledge score between the intervention classes and the control classes three months after the intervention. Unfortunately, limited evidence is available regarding the effects of the Kokkerelli Learning Street or comparable programmes on

participants' knowledge. In 2014, Kasten et al. performed a one-group effect evaluation of the Kokkerelli Learning Street (10). In this study, the outcome measure that changed most significantly was the determinant knowledge (mean difference T2-T0: 0.41, SD: 0.93). However, this study did not include a control group and the outcomes therefore only indicate within-group differences instead of between-group differences, while the present study does include a control group. The following assumptions were used for the sample size calculation:

- Children are nested within school classes, with 25 participants per class, and seven intervention classes and seven control classes;
- A significance level (alpha) of 0.05;
- A power of 80%;
- Independent samples t-test on difference in knowledge scores;
- An Intraclass Correlation Coefficient of 0.04, based on values used by Battjes et al. (8);
- A dropout rate of 10%, as based on dropout rates observed by Bartelink et al. (12);
- An SD of 0.24 for the mean change in absolute knowledge score (T2-T0) in the population, as based on the effect evaluation of a comparable programme by Battjes et al. (8).

With these assumptions, we can demonstrate an effect size of 0.104 on absolute knowledge scores. The standardised effect size is then equal to $0.104/0.22 = 0.47$, indicating a small to medium effect size (11).

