Teachers of participating school classes will be visited by Kids University for Cooking BV (intervention group) or researchers (control group) and they will receive a box with envelopes containing the three questionnaires (T0, T1, T2) for every child in their class. For each child, these questionnaires contain a unique ID number (equal for T0-T2 to allow for comparison over time) that cannot be traced back to the child. Teachers write the child's name on the envelope and at each time point, they distribute the right questionnaire to the right child. The questionnaires will be filled out in writing under supervision of the teacher, who will receive written and verbal instructions by researchers and/or employees of Kids University for Cooking regarding the questionnaire procedures. After the questionnaires are filled in, they are collected by the teacher and stored in a separate envelope in the box.

Data Processing and Statistical Analyses

After the T2 measurement, the envelopes with filled-in questionnaires are collected by Kids University for Cooking BV (intervention group) or researchers (control group). The envelopes with the ID number and name of the child, in which the blank questionnaires were stored, are not collected and will remain at the school to be destroyed. This means that only anonymised data will be collected; all non-anonymised data (envelopes with ID number and child's name) will remain at school to be destroyed. Researchers therefore only have access to the anonymised data. All anonymised data will be delivered to the principal researcher at Maastricht University.

In the data analyses, the mean scores of the answers on the questions will be used. Since single unrelated questions will be asked to test different aspects of knowledge, a score of correct answers will be used in further analyses of this determinant.

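### The taste score counts 'never tried' as the lowest degree of liking, so first tasting, which only the intervention arm is given, can raise the liking result by itself

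*Combined protocol and SAP*

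**What the plan says.** All references are to the combined protocol and SAP.

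- **Items.** Section 1.2 (questionnaire on psychosocial determinants): "Three questions are developed regarding the taste preferences", answered on a "scale from 1='never tried' to 6='I like it very much" range. The response of 21-11-2019 gives the same scale. One item is printed as an example, and the labels of codes 2 to 5 are not printed.
- **Scoring.** Section 1.2 (data processing and statistical analyses): "In the data analyses, the mean scores of the answers on the questions will be used". The only exception is knowledge, for which "a score of correct answers will be used in further analyses of this determinant". Also: "Questionnaire items for the determinants knowledge, intention, attitude, skills and taste preferences are combined into one variable per determinant for each time point".
- **Analysis.** Same section: "change scores (i.e., the difference in mean score between the baseline measurement and the follow-up measurements) will be calculated". A linear mixed model with group, time and their interaction follows. "Relative effect sizes will be calculated for each determinant", as Cohen's d with 0.2 as the benchmark for small.
- **Timing and exposure.** T0 comes before the introduction lesson. Table 1 of section 1.2 has the product's taste introduced in that lesson, and the children later eat the meal they cooked. Control classes complete the same questionnaires on the same timeline without the programme.
- **Question to be answered.** Section 1.1 lists liking of fruit and vegetables among the key questions.

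No section recodes 'never tried', sets it to missing or analyses it separately.

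**The concern.** Five of the six codes belong to children who have tasted the product; code 1 says only that the child has not. Averaging treats the step from 'never tried' to the lowest taster's answer as a one-point gain in liking. A child who tastes the product for the first time and gives that lowest answer therefore improves by 1 point on each affected item.

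If such steps were equally common in both arms they would largely cancel in the group-by-time term. The design makes them likely to differ, because tasting after T0 is supplied in one arm only. The taste result would then mix two things: more children have now tasted the product, and children like it more. The first is a legitimate programme effect, but it is not the liking effect that section 1.1 asks about. A reader of the reported Cohen's d could not separate them.

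**Working it through.** **1. Design inputs, checked on the plan's own figure.** Section 1.6 gives 7 classes per arm, 25 children per class, 10% dropout, ICC 0.04, SD 0.24 for the knowledge change, two-sided alpha 0.05 and 80% power.

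- Children per class after dropout: 25 × 0.9 = 22.5. Per arm: 7 × 22.5 = 157.5.
- Design effect: 1 + 21.5 × 0.04 = 1.86. Effective n per arm: 157.5 / 1.86 = 84.7.
- Detectable difference: (1.960 + 0.842) × 0.24 × √(2/84.7) = 0.103 (0.104 with t quantiles). The stated 0.104 is reproduced.

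That figure concerns knowledge. The documents give none for taste, so the rest rests on assumptions.

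**2. The shift.** Let p be the share answering 'never tried' at T0, u the share of those who first taste in the intervention arm, and k the number of items affected (1 to 3). If controls do not newly taste and new tasters answer code 2:

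shift in mean score = p × u × k/3.

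With complete data and no added covariates, the planned model's T0–T2 interaction is the difference in mean change, so the shift passes straight into it.

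**3. Assumptions for scale.** Prior tasters spread evenly over codes 2–6 (mean 4, variance 2). Retest correlation 0.5, so their change variance is 2 × 2 × (1 − 0.5) = 2. The ICC of 0.04 is borrowed from knowledge.

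- Baseline variance: 2(1 − p) + 9p(1 − p).
- Change variance: 2(1 − p) + (k/3)² × pu(1 − pu) in the intervention arm, 2(1 − p) in control.
- Chance of p<0.05: class-level comparison, noncentral t on 12 df. This approximates the three-level model.

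**Worked case: p = 20%, u = 1, k = 3.** Shift = 0.20. Baseline SD = √(1.60 + 1.44) = 1.74, so d = 0.20/1.74 = 0.11. Change variances are 1.60 + 0.16 = 1.76 and 1.60. SE = √((1.76 + 1.60) × 1.86/157.5) = 0.199. Noncentrality = 0.20/0.199 = 1.00, which gives 15%.

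| Scenario | p = 10% | p = 20% | p = 30% |
|---|---|---|---|
| Three items, full uptake: d | 0.06 | 0.11 | 0.17 |
| same: chance of p<0.05 | 7% | 15% | 31% |
| same, change variance held at 2 for everyone (plus the shift term) | 7% | 13% | 24% |
| Three items, 50% uptake: chance | 6% | 8% | 12% |
| One item, full uptake: d | 0.02 | 0.04 | 0.06 |
| same: chance | 5% | 6% | 8% |

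The third row matters because the base case gives children who stay at 'never tried' no change variance, so noise shrinks as p grows.

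**4. Sensitivity (three items, full uptake).** ICC 0 gives 9/24/51%; ICC 0.10 gives 6/11/20%. If 20% of never-tried controls also taste, the chances are 6/11/21%.

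**5. Would setting 'never tried' to missing do?** The plan says of the mixed model that "it naturally handles missing values, in case data are missing at random". Here the T0 value would be missing because the child had not tasted, and new tasters would enter after baseline, mainly in one arm. Large-sample maximum likelihood (T0, T1, T2, unstructured covariance, class intercept left out, p = 20%, full uptake, prior tasters averaging 4) gives a false shift of −0.13, −0.07, 0.00 and +0.07 when new tasters average 2, 3, 4 and 5. It is unbiased when new tasters rate like prior tasters; otherwise the sign depends on how they differ.

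**6. Children with 'never tried' on only some items.** In simulation (1,500 trials per p, 'never tried' on one, two or three items at random, no change in liking on items already tasted), the planned mean shifts by 0.07/0.14/0.20 for p = 10/20/30%. Keeping to the items with a liking answer at T0 stays within 0.005 of zero. Letting the item set change between time points gives −0.07/−0.14/−0.22.

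**The case against.** **The effect may be negligible here.** The shift needs a non-zero never-tried share and more new tasting in the intervention arm than in control. The nine products include tomato, carrot and strawberry, no share is given, and control children may taste the product elsewhere. Only one of the three items is printed, so it is not shown that all three can start at 'never tried' for the same child. This stands: the concern is conditional, and with one item affected the error rate is close to nominal.

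**Tasting is part of the programme.** True, so exposure deserves to be reported, but under its own name.

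**The questionnaire was piloted.** Section 1.2 calls it appropriate after small adaptations. Section 1.6 describes the earlier evaluation as one-group, so it could not show a difference between arms caused by coding.

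**Stronger readings that the documents do not support.**

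- A reader might infer a near-medium artefact. If 20% were new tasters answering code 4 and the SD were 1.25, the shift would be 0.20 × 3 = 0.60 and d 0.48. Part of that rise may be genuine liking, so it cannot all be called false.
- A reader might infer that a false-positive result is likely. At a 50% never-tried share the base case gives 80%, but nothing in the documents supports that share, and the figure falls to 54% with change variance held at 2.
- A reader might infer that treating 'never tried' as missing must bias the result downwards. That holds only if new tasters rate below prior tasters.

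The intention scale also starts at a non-ordered answer ('I don't know'). That is a related scoring question and is not assessed here.

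**Conclusion.** The concern holds in conditional form. Followed as written, the plan can count first tasting as increased liking whenever some children have not tried the product at T0 and new tasting is more common in the intervention arm. Each new taster then adds at least 1 point per affected item, whatever they think of the taste.

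The size cannot be fixed from the documents, because the never-tried share, uptake, number of items affected and taste SD are not given. Under the assumptions shown, d stays below the plan's benchmark for small at shares up to 30%. The error rate runs from nominal to about three times nominal at a 20% share (15% against 5%), and to 24–31% at a 30% share. The issue is confined to the taste result, which answers a stated key question. It should be fixed, but it does not threaten the main conclusion on knowledge.

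**What to change.** Set before analysis:

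1. Take 'never tried' out of the numeric taste score. Report 'has tried' by arm and time as a separate outcome.
2. Analyse mean liking on the remaining codes in children with a liking answer at T0, using at every time point only the items that had a liking answer at T0. Name this as the analysis that answers the liking question, for prior tasters.
3. Optionally add, as supportive, an all-children analysis of 'tried and likes it' against all other answers. Fix the cut-point from the questionnaire's own labels, and fix the rule for combining the three items. State that this outcome also rises when tasting only reveals liking that was already there.
4. Do not rely on setting 'never tried' to missing in the mixed model as a substitute.

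The cost is recoding of answers the plan will already collect and a small added analysis; the questionnaire need not change. The downside is that children who had not tasted the product at T0 leave the mean-liking analysis, so it speaks only for prior tasters. If those children answer 'never tried' on all three items, the whole never-tried share is lost from it. In the simulation with partial answers the loss was 3/7/10% at shares of 10/20/30%.

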Measures in the intervention group are performed before the start of the introduction lesson (T0), directly after finishing the evaluation lesson (T1) and three months after the evaluation lesson (T2). In the control group, a similar timing of the measurements will be utilised. At baseline, participants' demographic characteristics (age in years, gender (1=male, 2=female), (parental) birth country (1=western, 2=non-western) are collected via child-reported questionnaire. At all timepoints, children are asked to answer a short questionnaire assessing their psychosocial determinants (knowledge, taste preferences, intention, skills, and attitude) related to the food product that they encountered during their participation in the Learning Street.

Psychosocial Determinants - Questionnaire

Changes in psychosocial determinants of fruit and vegetable intake are selected as outcome measures. Based on the EnRG framework, other literature and the aims of the Learning Street, five relevant determinants are selected: (i) knowledge; (ii) taste preferences; (iii) intention; (iv) skills; and (v) attitude (1–4). Children's knowledge will be assessed by six questions based on what they were taught during the Learning Street.

Three questions are developed regarding the taste preferences (e.g., '*What do you think about the taste of the food product?*') (scale from 1='never tried' to 6='I like it very much'). Questions assessing intention concern participants' plans to consume or cook a meal containing the specific food product in the future and will be assessed on a scale from 1='I don't know' to 6='yes I will'. For skills, children are asked if they are able to cook a meal with the specific food product ('I don't know', 'no', 'a little', 'yes'). Questions and scales for attitude ('*How much do you think the target behaviours are clever/interesting and nice/cool/tasty?*') are used as described by Ajzen and Fishbein and as previously used in comparable research. They are formulated in a way that is simple and understandable for children (scale from 1='no, not at all' to 5='yes, totally') (5,6). The questionnaires were previously used in a pilot study on the Learning Street (7) and appeared appropriate after small adaptations.

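### Intention is scored with 'I don't know' as its lowest point, so any loss of uncertainty counts as improvement; skills may share the fault, because its codes are not stated

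*Combined protocol and SAP*

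**What the plan says.** The questionnaire part of section 1.2 states that intention "will be assessed on a scale from 1='I don't know' to 6='yes I will". Points 2 to 5 have no labels, and no negative answer is shown. For skills, "children are asked if they are able to cook a meal with the specific food product ('I don't know', 'no', 'a little', 'yes" are the options, in that order and without numeric codes. The reply to the committee of 21-11-2019 describes both scales in the same way.

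The other scales show their numbers. Attitude has a "scale from 1='no, not at all' to 5='yes, totally", so a true negative is at the bottom. Taste preference has a "scale from 1='never tried' to 6='I like it very much".

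On scoring, the data processing part of section 1.2 says: "In the data analyses, the mean scores of the answers on the questions will be used". Only knowledge is treated differently, as a count of correct answers. It adds: "Questionnaire items for the determinants knowledge, intention, attitude, skills and taste preferences are combined into one variable per determinant for each time point". Change from baseline is then calculated, and a three-level linear mixed model with a group-by-time term estimates the effect, expressed as Cohen's d with 0.2 called small. Nowhere is 'I don't know' recoded, set to missing or analysed separately.

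**The concern.** Being undecided is not the lowest degree of intention. A child who does not want to eat or cook the product intends less than one who has not made up their mind. The stated intention scale puts the undecided child at the bottom, and the mean score and linear model then treat every step upward as a gain.

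Using the same questionnaire in both arms removes this only if 'I don't know' falls equally in both. That is doubtful here. The Learning Street lets children taste the product, see it grown, cook it and eat it (section 1.2, Table 1), while control classes complete the questionnaires with no such contact. A larger fall in uncertainty among intervention children goes directly into the group-by-time estimate, whichever way those children decide.

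Intentions and skills are two of the six key questions in section 1.1. Section 1.7 says the evaluation is meant to support entry in the Dutch database for effective interventions. A positive finding on intention could then partly reflect familiarity and not willingness.

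**Working it through.** The plan gives no figure on this point, so there is none to reproduce. The check is arithmetic on the stated codes, followed by an illustration.

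**From the documents (section 1.2):** intention code 1 = 'I don't know' and code 6 = the firm yes; skills options in listed order; averaging of answers; d = 0.2 as a small effect.

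**Assumed, because the documents do not say:** the excess share p of intervention over control children who move one step up from 'I don't know' (10%, 20%, 30%); an SD of 1.5 for intention and 0.9 for skills; a negative answer one step above 'I don't know'; skills coded 1 to 4 as listed; and a shift on every item of the determinant.

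**Step 1, intention, one child.** Gain = new code - 1. The smallest gain is 2 - 1 = +1 and the largest 6 - 1 = +5. A negative answer at any point from 2 to 5 gives +1 to +4. A child who softens from that answer to undecided loses the same amount. The direction follows from the stated code alone, provided that a negative option exists.

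**Step 2, skills, one child.** With codes 1, 2, 3, 4 in listed order, moving from 'I don't know' to 'no' gives 2 - 1 = +1 on a range of 4 - 1 = 3. If 'I don't know' is set to missing, this gain disappears. If it is placed between 'no' and 'a little', the move scores -1. The result for skills therefore depends on a coding that is not stated.

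**Step 3, group difference.** False mean difference = p x 1 point; d = p / SD.

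| Excess share p | Mean difference | d, intention (SD 1.5) | d, skills (SD 0.9) |
|---|---|---|---|
| 10% | 0.10 | 0.10/1.5 = 0.07 | 0.10/0.9 = 0.11 |
| 20% | 0.20 | 0.20/1.5 = 0.13 | 0.20/0.9 = 0.22 |
| 30% | 0.30 | 0.30/1.5 = 0.20 | 0.30/0.9 = 0.33 |

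For either determinant, SDs from 0.8 to 1.5 give d from 0.20/0.8 = 0.25 down to 0.20/1.5 = 0.13 at p = 20%.

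**Step 4, dilution.** Intention has more than one question, but the number is not given. If only one of k items shifts, the difference is p/k. With k = 2 (assumed) and p = 20%, it is 0.10 points, and d = 0.10/1.5 = 0.07.

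**The case against.** A reader might infer that two of the five determinants are shown to count a firm 'no' as improvement. The documents do not support that. Skills has a listing order but no codes, although every other scale shows numbered end points. For intention, no negative option is printed, so placing one at point 2 is inference. What remains is narrower: intention explicitly puts 'I don't know' lowest, so any negative option must score above it. If there is none, an unwilling child has no fitting answer.

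A reader might also infer that the artefact would by itself produce the plan's small effect. At the assumed SD of 1.5, intention gets there only at the 30% end and only if all items shift. Skills gets there at 20%, but on the unstated coding. The documents give no SD and no baseline rate of 'I don't know' for either scale.

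Nor can a favourable result be written off as spurious. Children who cook and eat the product may well move from 'I don't know' to a positive answer, which is a real gain.

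Section 1.2 reports that the questionnaires were piloted and found suitable after small changes. Section 1.6 describes that pilot as a one-group evaluation, so it could not show a shift that differs between arms.

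Finally, replacing the score with a yes/no main analysis would be a poor trade. The cut-point cannot be set without the labels of points 2 to 5, and a median split of a roughly normal score keeps only about 2/pi = 64% of the information. This objection stands, and a proportion belongs in a sensitivity analysis.

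**Conclusion.** The point holds, explicitly for intention and probably for skills. Under the stated intention coding, every move away from 'I don't know' counts as improvement, and the plan has no rule that prevents a larger fall in the intervention arm from appearing as a programme effect. For skills the same follows only if the options are numbered as listed.

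The size is unknown. The illustrated ranges, d about 0.07-0.20 for intention and 0.11-0.33 for skills, rest on all the assumptions listed in the working and are not estimates. Knowledge, the outcome behind the sample size in section 1.6, is scored as correct answers, so neither it nor the power calculation is affected. The change is worth making because it concerns two key questions and needs no new data.

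**What to change.** Before any outcome data are seen, the analysis section should:

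- State the numeric codes and labels for every intention and skills answer.
- Take 'I don't know' out of the ordered score, so that it never ranks below a negative answer. Score intention over the substantive answers only, and skills as no / a little / yes. Say how a child's score is formed when some or all items are 'I don't know'.
- Keep the planned three-level model for that score.
- Report the proportion answering 'I don't know' by arm and time point.
- Add a sensitivity analysis on the proportion answering positively, counting 'I don't know' as not positive so that no child is dropped. Fix the cut-point from the actual questionnaire labels, state how several intention items become one proportion, and keep the class level in the model.

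The cost is wording and scoring, with no new data. Some precision is lost where 'I don't know' answers leave the score. The main score then describes children who gave a substantive answer and relies on the model's missing-at-random assumption for the rest, which is why the sensitivity analysis should include everyone. Scores will be less directly comparable with the pilot.
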